8.8 CONTINUATION OF TREATMENT

No further provisions are made for access to the study treatment under this protocol following Day 84/Visit 6.

9 ENROLMENT AND RANDOMISATION PROCEDURES

Full details of procedures will be provided in the Investigator Site File and eCRF Completion Guidelines.

9.1 SCREENING (Visit 1)

Subjects will be evaluated according to the inclusion and exclusion criteria (Sections 7.3.1 and 7.3.2). Subjects will be deemed eligible for randomisation if all inclusion criteria and no exclusion criteria are met. The Investigator is required to document all screened candidates considered for inclusion in this study. If excluded prior to enrolment, the reasons for exclusion will be documented in the subject's eCRF, medical notes and on the study screening log.

A subject may be retested once for screening laboratory criteria that do not meet protocol in/exclusion criteria initially, so long as randomisation occurs no more than 21 days from the initial Screening visit date (if eligible based on retest results).

A subject may be re-screened after an initial screening and screening failure once it is assessed by the investigator the reason for the screening failure was resolved e.g.: Subject screening failure due to folates outside of protocol range, receives folates replacement therapy can be re-screened.

9.2 RANDOMISATION (Visit 2)

Subjects will be registered into the study at the Screening visit and assigned a unique subject identification number in the IRT. Subjects will be categorised during the screening process based upon their age (2 to \leq 9 years of age and 10 to \leq 17 years of age) and their gender. Age and gender will be incorporated into the randomisation as stratification factors. A minimum of 18 subjects must be recruited into the 2-9 and 10-17 age group and a minimum of 25% of either sex must be recruited. Maximum of 12 subjects will be recruited in the 1 m - 2 yrs cohort. In the event of a subject having a birthday whilst on study and they move to a different age cohort -they will remain in the baseline cohort for the duration of the study.

A final eligibility evaluation must be conducted by the Investigator/designee prior to randomisation/pre-assignment PK visit via IRT, once the results of all Screening assessments are available.

Subjects aged 1 month to < 2 years:

Following the eligibility evaluation, a maximum of 12 subjects will enter a Pre-assignment phase: 1-day Pharmacokinetic assessment day following a single dose of 0.1 ml/kg ferric maltol oral suspension. Once the PK samples have been analysed and evidence is showing metabolism and elimination of maltol, subjects will be assigned to ferric maltol oral suspension treatment phase. Subjects will be eligible to enter the treatment phase if their maltol level returns to baseline, or to a level confirming there is no accumulation of maltol

CONFIDENTIAL Page 52 of 80

or maltol glucuronide. The sample results will be analysed on an individual basis. The Sponsor's Medical Monitor will make a recommendation to the investigator based on preassignment results. The investigator will make the final decision if subjects aged 1 month to < 2 years are eligible to enter the treatment phase.

Subjects aged 2 years to 17 years:

No subject may begin treatment prior to being randomised in the IRT. The randomisation procedure (created using a computer-generated random permutation procedure) will assign the subject to one of the treatment arms.

Initial dosing with ferric maltol and ferrous sulfate must occur on the same day of randomisation. The date of Visit 2 is the date of first dose with ferric maltol or ferrous sulfate.

9.3 REPLACEMENT POLICY

Discontinuations after randomisation due to adverse events will not be replaced. Discontinuations after randomisation for any other reasons may be replaced at the discretion of the Sponsor, in order to reach the agreed number of evaluable subjects for pharmacokinetic endpoints.

9.4 BLINDING PROCEDURES

Not applicable as this is an open label study.

9.5 EMERGENCY UNBLINDING

Not applicable as this is an open label study.

CONFIDENTIAL Page 53 of 80

10 STUDY PROCEDURES

10.1 COVID-19 IMPLICATIONS ON THE TRIAL

All efforts will be made by the Investigational sites to avoid screenings of any subjects who might have a known exposure to SARS-CoV-2 or any symptoms suggestive of any infection with it by following the local guidelines provided for evaluating patients for COVID-19.

If there is a confirmed COVID-19 positive case (SARS-CoV-2-RT-PCR) in a subject after randomization, the subject will be assessed by the investigator to determine if their participation in the trial is suitable. Positive cases will be recorded as an adverse event in the CRF, and authorised medication will be recorded as concomitant medication in the CRF.

[figure not shown]
Every attempt will be made to follow up with the adverse events via phone call to the subject until known resolution or stabilization of the disease.

During periods of time when a pandemic impedes the ability of patients to travel to the study site

- Study assessments and visit window may be expanded up to 14 days (Visit 4, 5, 6)
- Study assessments by a healthcare professional may occur at an offsite location such as the patient's home.

Where applicable country and local regulations and infrastructure for home healthcare allow, home healthcare may take place at a location other than the clinical trial site to perform study assessments, which may include but are not limited to collection of blood and urine samples, measurement of vital signs, length/height, and weight.

10.2 DESIGN SCHEMATICS

 $^{^{1}}$: Only applicable if subjects aged 1 month to < 2 years continues to the assigned treatment phase.

²: Visit 3 will only be performed for the first 12 subjects in age group 2-17 years

10.3 SCHEDULE OF ASSESSMENTS FOR SUBJECTS AGED 2 YEARS-17 YEARS

	SCREENING	TREATMENT					FOLLOW-UP
Duration	Up to 21 days	12 WEEKS (equivalent of 84 days)					10-14 days
Day		1	7-10	28	56	84	94-98
Visit ¹¹	1	2	3 ³	4	5	6	7 ^{9,10}
Informed Consent	х						
Eligibility ^{1,8}	х	х					
Demographics	х						
Medical History	х						
Physical Examination	х					х	
Vital Signs ²	х	х	Х	X	х	х	
Urine Pregnancy Test ⁴	х	х	х	х	х	х	
Clinical Laboratory tests ⁵	х					х	
Haematology ⁶	х			X		х	
Iron markers ⁶	х			Х		Х	
PK assessment PK Blood Sampling for maltol/maltol glucuronide and iron markers ⁷		х	х				
Randomisation ⁸		х					
Dispense Study Drug		х	х	х	х		
Return Study Drug for Accountability			х	х	х	х	
Palatability questionnaire		х		х			
Adverse Events		х	х	х	х	х	х
Concomitant Medications and Procedures	х	х	х	х	х	x	х
Compliance reminder		х	х	Х	х	х	
Compliance assessment			х	Х	х	Х	

CONFIDENTIAL Page 56 of 80

- 1. A subject may be retested once for laboratory criteria that do not meet protocol criteria so long as randomisation occurs no more than 21 days from the initial screening visit date (if eligible).
- 2. Vital Signs body weight, height, systolic/diastolic blood pressure, pulse, and body temperature at each visit. Patient weight should be recorded at each clinic visit and drug dosing administered as per last clinic visit weight.
- 3. Visit 3 (PK Day 2) only applicable for the first 12 subjects randomised to ferric maltol group in each age group (2 yrs -9 yrs, 10 yrs-17 yrs).
- 4. Urine pregnancy test for female subjects of childbearing potential only.
- 5. Clinical Laboratory tests including:
 - a. Clinical Chemistry: Vitamin B12, folate, ALT, AST, alkaline phosphatase, gamma-glutamyl transpeptidase (GGT), total bilirubin, creatinine, amylase, blood urea nitrogen (BUN), phosphorous, sodium, potassium, chloride, calcium, total cholesterol, uric acid, glucose, total protein, albumin
- 6. Haematology and Iron markers:
 - a. Haematology: Red blood cell count, haemaglobin, haematocrit, mean cell volume (MCV), white blood cell count (total and differential (% and absolute), absolute reticulocyte count and platelet count.
 - b. Iron Markers: serum iron, transferrin, transferrin saturation (TSAT), total and unsaturated iron binding capacity (TIBC, UIBC) and ferritin.
- 7. On PK study Day 1 (Visit 2) and PK study Day 2 (Visit 3) for the first 12 subjects in each age group (2 yrs 9 yrs, 10 yrs-17 yrs, respectively) who have been randomised to ferric maltol groups have baseline PK blood samples collected immediately prior to ferric maltol dosing (0 hr). Subjects will then have further PK blood samples collected at two (2) additional times between 0.5 hr and 6 hrs after dosing on Visit 2 and 3; the post-dose PK sample time collection windows will be 0.5-1h, 1.0-2.0 hrs, 2.0-3.0 hrs, 3.0-4.0 hrs and 4.0-6.0 hrs. For each individual subject, the post-dose PK blood sampling schedule will be the same on PK Day 1 and PK Day 2. Post-dose blood samples should be collected within the time windows allocated only. N.B: samples should be taken at least 1.0 hr apart.
 - In the event of an administered dose not being consumed or partially consumed by the patient this will be noted as a missed dose and will not be repeated.
- 8. Eligibility laboratory sampling/assessments must be completed before the subject is randomised and before the first dose of study treatment taken. A minimum number of 18 subjects must be recruited into each age group (2 yrs -9 yrs, 10 yrs-17 yrs) and a minimum of 25% of either sex must be recruited and at least 49 subjects per arm.
- 9. Subjects who have at least one dose of study medication and withdraw earlier from the study undergo Visit 7 (Day 94-98) assessments (excluding those who have withdrawn consent).
- 10. Visit 7 is conducted by telephone, unless the Subject has an ongoing AE that requires physical examination or investigations for assessment/management. Visit 7 will take place 10-14 days after Visit 6 (Week 12) unless subject discontinued treatment early. All withdrawn subjects should undergo Visit 7 within 10-14 days after the last dose of study drug (if the subject agrees in the case of withdrawn consent).
- 11. Visit Windows: Maximum of 21 days between screening and randomisation. The Subject must visit to complete:
- a. Visit 2 and Visit 3: must be 6-9 days between the scheduled PK days.
- b. Visit 4: +/- 5 days relative to date of Visit 2/first dose administered
- c. Visits 5 to 6: +/- 5 days relative to date of Visit 2/first dose administered
- d. Visit 7: 10-14 days after Visit 6 (unless subject discontinued treatment early see Note 10

CONFIDENTIAL Page 57 of 80

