In the Phase 1 paediatric PK study, children and adolescents aged 10 to 17 years were administered up to the adult dose of 30 mg BID. Given physiological control of intestinal absorption of iron uptake through the hepcidin pathway and considering a total daily dose of 60 mg iron is within the approved dosage regimen for oral ferrous products in older children, iron overload in a 10-day exposure was considered not to be a risk. Furthermore, in children the metabolism of maltol through glucuronidation in the liver was similar to adults. There was not any great individual clinical benefit over 10 days of ferric maltol therapy, although the information gathered was very important in establishing the doses to be studied in this subsequent Phase 3 paediatric efficacy and safety study in IDA subjects.

Doses chosen for this phase 3 study were based on the first Paediatric PK study and a new age-appropriate formulation has been developed. The study population will recruit subjects with iron deficiency anaemia who are otherwise generally well. The study population will include both female and male subjects aged 1 month - 17 years age range.

From the Phase I PK adult study comparing the ferric maltol suspension and ferric maltol capsule under fed and fasted condition, information was gathered that in the fed condition, ferric maltol capsule and suspension had similar PK with respect to serum iron C_{max} and AUC_{last} .

The C_{max} data suggest that there might be a formulation effect in the fasted state in favor of the capsule with respect to serum iron levels but this was not definitively supported by AUC_{last} and AUC_{inf} comparisons, nor was this supported by the maltol and maltol glucuronide PK.

Ferric maltol suspension had similar PK when administered in fasted or fed conditions with respect to Cmax and AUClast. Nevertheless, we advise ferric maltol should be taken at least 30 mins after meal.

PK assessments will take place for the first 12 subjects in age group 2 yrs -17 yrs) and all 1 m - < 2 yrs assigned to ferric maltol to assess the efficacy, the safety and tolerability of ferric maltol.

This study's procedures risks are related to IV cannulation and blood sampling, with fainting, minor bleeding and bruising regarded as the main risks. Total blood loss as a result of phlebotomy will be approximately 33.8 ml in subject group 1 m to less than 2 years and 40 ml in the 2 to 17 yrs age group.

CONFIDENTIAL Page 37 of 80

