6.3 PRIMARY ENDPOINTS

- Safety and gastrointestinal tolerability
 - Treatment emergent Adverse Events (TEAE)
 - Treatment-emergent Serious Adverse Events (TESAEs) Treatment-emergent Adverse Events leading to premature discontinuation of study drug/PK assessments from baseline to Week 12
- Change in Hb concentration from baseline to Week 12

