Subjects aged 2-17 will be randomised 1:1 to receive ferric maltol oral suspension or ferrous sulfate oral liquid. The first 12 subjects randomised to ferric maltol in each age sub-groups (2 – 9 yrs, 10 – 17 yrs, respectively) will enter a Pharmacokinetic phase from Visit 2 (PK Day 1) till Visit 3 (PK Day 2) with 2 PK days. Following baseline pre-dose blood sample, subjects will take a single dose of 2.5 ml (2 yrs -11 yrs) or 5 ml (12 yrs - 17 yrs) ferric maltol oral suspension under supervision and then a further 2 PK blood samples will be taken up to 6 hours. Following the last scheduled PK sample on PK Day 1 (Visit 2), subjects will be reminded to take their dose twice daily until PK Day 2 (between Day 7-Day 10). On PK Day 2 (Visit 3) subjects should withhold their morning dose until attending their second PK assessment day. Same procedure will be repeated for PK assessment as on PK Day 1. Following PK Day 2, subjects will continue treatment until Week 12.

Once the 12 subjects in each age subgroup (2 - 9 yrs, 10-17 yrs, respectively) have finished their PK visits, they will continue on treatment until week 12. Further subjects will not need to have PK samples taken.

Subjects randomised to ferrous sulfate oral liquid will not need to complete the PK period, they will remain on oral ferrous sulfate until Week 12. Ferrous sulfate 125 mg/ml (25 mg/ml elemental iron) or equivalent dose will be used for all children/adolescents. To maximise the iron replenishment for subjects within this group as well; aged 2 - 17 yrs will be dosed 0.24ml (6mg elemental iron) per kg body weight, up to a maximum of 8ml given daily in two divided doses.

 Assigned treatment phase: 12 weeks open label treatment for ferric maltol children aged 1 month to less than 2 years

Once the PK samples have been analysed for subjects aged 1 month to less than 2 years and they can enrol in the randomisation phase, they will be assigned to receive ferric maltol oral suspension and start the 0.1 ml/kg/dose, BID on Visit 2 for 7-10 days. On Visit 3 (PK Day 2), following baseline pre-dose blood sample and urine sample, subjects will take a single dose of 0.1 ml/kg ferric maltol suspension under supervision and then a further three PK blood samples and urine samples will be taken at three timepoints up to 12 hours. Subjects will continue treatment until week 12.

- End of study: Week 12 visit

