11 SAFETY

11.1 DEFINITIONS

11.1.1 ADVERSE EVENT (AE)

An AE is any untoward medical occurrence in a subject administered a pharmaceutical product and does not necessarily have a causal relationship with this treatment. An AE can therefore be any unfavourable or unintended sign or symptom, intercurrent illness, injury, or any concomitant impairment of the subject's health, temporally associated with the use of a medicinal product, whether or not considered related to the medicinal product.

A treatment-emergent AE is any AE temporally associated with the use of a study drug, whether or not considered related to the study drug.

AEs include:

- Exacerbation of a chronic or intermittent pre-existing condition/disease/symptom
 present at baseline that worsen during the study including either an increase in
 frequency and/or intensity.
- Disease or medical condition detected or diagnosed after study drug administration even though it may have been present prior to the start of the study.
- Events considered by the Investigator to be related to study-mandated procedures.
- Abnormal safety assessments, e.g. laboratory test abnormalities, physical exam findings or vital sign measurements must be reported as AEs if they represent a clinically significant finding in the medical and scientific judgment of the Investigator, symptomatic or not, which was not present at baseline or if present at baseline, worsened during the course of the study or led to dose reduction, interruption or permanent discontinuation of study drug. However, if an abnormal laboratory or other safety-related test result is associated with clinical signs or symptoms, the signs or symptoms should be recorded as an AE. If signs and symptoms are part of a diagnosis, then the diagnosis should be recorded as AE.
- Signs, symptoms of a suspected drug interaction.
- Signs, symptoms of a suspected overdose of either the study drug or a concomitant medication (overdose per se will not be reported as AE/SAE).

AEs do not include:

• Medical or surgical procedure, e.g., surgery, appendectomy, endoscopy, tooth extraction, transfusion (as these are treatments for an AE). However, the event resulting in the procedure is the AE (e.g. appendicitis, abdominal pain).

CONFIDENTIAL Page 65 of 80

- Pre-existing disease or medical condition documented at baseline that does not worsen.

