11.2 REPORTING AND DOCUMENTATION

AEs should be documented in terms of a medical diagnosis. When this is not possible, the AE should be documented in terms of signs and/or symptoms observed by the Investigator or reported by the subject at each study visit.

Any pre-existing conditions or signs and/or symptoms present in a subject prior to the start of the study should be recorded on the Medical History CRF.

All SAEs that occur after informed consent through to study completion (Follow-up visit) or premature discontinuation must be reported on the SAE form in the CRF and reported within 24 hours to the Sponsor using the Shield SAE form. All AEs occurring from the time of the first dose of study treatment through study completion (Follow-up visit) or premature

CONFIDENTIAL Page 67 of 80

discontinuation must be reported on the AE form in the CRF. For AEs related to COVID-19 testing, see section 10.1.

Any SAE that occurs during the clinical study or within two weeks of receiving the last dose of study drug, whether or not related to the study drug, must be reported to the Sponsor.

Deaths or congenital abnormalities if brought to the attention of the Investigator AT ANY TIME after cessation of study drug AND considered by the Investigator to be possibly related to study drug, should be reported to the Sponsor.

At each visit AEs will be solicited. The nature of each event should be established. Details of changes to study drug dosing or any subsequent treatment should be recorded on the appropriate pages of the CRF.

AEs already documented in the CRF (i.e., at a previous assessment) and designated as 'ongoing' should be reviewed at subsequent visits as necessary. Upon resolution, the date of resolution should be recorded in the CRF. If an AE increases in frequency or severity during a study period, a new record of the event should be started. If the AE lessens in intensity, no change in the intensity is required as only the worst intensity must be reported.

All AEs and SAEs, including those that are ongoing at the end of the study or at premature discontinuation, will be followed up until resolution or stabilisation or until the event is otherwise explained.

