2.2.4 Sample Size Determination

In total up to 110 patients will be recruited into the study. Up to 98 subjects will be randomised in the 2 -17 years cohort and up to 12 subjects will be assigned in the <2 years cohort.

The aim is to recruit up to 49 subjects in each treatment group in the 2 – 17 years cohort. At least 12 subjects in each age group respectively (i.e. 24 subjects in total) will be included in the PK analysis group in the ferric maltol oral suspension group. A sample size of 49 in the Ferric Maltol group provides at least 80% power to demonstrate that the lower bound of the 95% confidence interval for increase in Hb at 12 weeks, compared with baseline, is above zero. This assumed that the standard deviation (SD) of the change from baseline is 1.2 g/dL or lower and the true mean change is at least 0.5 g/dL.

Every effort will be made to recruit up to 12 subjects in the under 2's age group but in case of reasons of feasibility it cannot be completed, then the study may be completed without that cohort.

If less than 91 subjects in total have been randomised when 32 ferric maltol subjects have completed treatment (or withdrawn from the study), then an interim analysis of the primary effectiveness endpoint (change in Hb concentration from baseline to Week 12) will be conducted. If significant, the study will stop recruitment. If not significant, the study will continue (all subjects will be assigned to ferric maltol) until 54 subjects have been recruited in the ferric maltol arm.

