3.6 Safety Assessment

Safety data will be summarised by actual treatment received (and in total for selected analyses) based on the Safety Population.

Safety and gastrointestinal tolerability will be compared between ferric maltol oral suspension and ferrous sulfate oral liquid via the incidence of TEAEs, TESAEs and TEAEs leading to premature discontinuation of study drug, estimated as the number of subjects with at least one event divided by the number of subjects in the Safety Population.

Adverse Events (AEs) will be categorised by primary system organ class and MedDRA preferred term as coded using the MedDRA dictionary version 24.0. The number, intensity, relation to study medication and action taken will be described by incidence tables. Serious Adverse Events (SAEs) will be listed and tabulated separately.

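### Only ferric maltol children in the PK subset are asked about adverse events at Day 7-10, so the primary tolerability comparison has unequal timing of ascertainment

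*Protocol*

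**What the plan says.** **Who attends.** Note 3 to the 2-17 year schedule (Protocol 10.3, repeated under SAP Table 2.1) restricts Visit 3, PK Day 2, to children in the PK subset: "for the first 12 subjects randomised to ferric maltol group in each age group (2 yrs -9 yrs, 10 yrs-17 yrs". In the comparator arm, "Subjects randomised to ferrous sulfate oral liquid will not need to complete the PK period" (Protocol 7.1). SAP 2.2.4 sizes the subset: "At least 12 subjects in each age group respectively (i.e. 24 subjects in total) will be included in the PK analysis group".

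**What happens there.** The Visit 3 column marks adverse events, PK sampling, drug dispensing and return, a compliance reminder and a compliance assessment. Protocol 11.2 makes each visit an active enquiry: "At each visit AEs will be solicited".

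**What counts.** The list of what is an adverse event in Protocol 11.1.1 includes "Events considered by the Investigator to be related to study-mandated procedures". Protocol 5.6 says that the procedural "risks are related to IV cannulation and blood sampling, with fainting, minor bleeding and bruising regarded as the main risks". SAP 3.6.1 treats any event starting after the first dose as treatment-emergent, whatever its cause.

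**How it is compared.** SAP 3.6 compares the arms by incidence, "estimated as the number of subjects with at least one event divided by the number of subjects in the Safety Population". SAP 3.1.5 makes this descriptive only.

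**The concern.** Comparing tolerability between the arms is the first primary objective, and the measure is a yes/no count per child. Such a count depends on how often and how soon each child is asked. Here the extra question and the extra needles come with the assigned treatment, so randomisation does not balance them. A mild stomach upset in the first week is asked about after 6 to 9 days in about half of one arm. In the rest of that arm and in all of the other, it is asked about after roughly four weeks. Bruising or fainting from PK sampling can occur only on ferric maltol. At stake is the reading of the headline TEAE incidences: part of any difference could come from the visit schedule and not from the drug.

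**Working it through.** **1. The plan's own figure.** 12 children per age group × 2 age groups = 24, as SAP 2.2.4 states. With 49 planned per arm (SAP 2.2.2), Visit 3 applies to 24/49 = 49% of ferric maltol and 0/49 = 0% of ferrous sulfate children.

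**2. Scheduled adverse event contacts (Protocol 10.3).** A PK child has Visits 2, 3, 4, 5, 6 and 7 = 6. Every other child has Visits 2, 4, 5, 6 and 7 = 5.
- Ferric maltol average: (24 × 6 + 25 × 5)/49 = 269/49 = 5.49.
- Ferrous sulfate average: 5.00.
- Ratio: 5.49/5.00 = 1.098, or 9.8% more.

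**3. First question after Visit 2 (Protocol 10.3, note 11).** PK children: 6 to 9 days later. All others: Visit 4, Day 28 ± 5, that is Day 23 to 33.

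**4. Extra procedures (Protocol 10.8.6).** 3 timepoints × 2 PK days = 6 samplings, or 6 × 4.5 ml = 27 ml. The first is pre-dose on Day 1, so 6 − 1 = 5 follow the first dose and can give rise to a TEAE.

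**5. Possible shift in incidence.** The documents give no figure for the effect of PK participation, so the following is an assumption. If it raises a child's chance of at least one recorded TEAE by x, the arm difference with no true drug difference is (24/49) × x:

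| Assumed x | Shift at 24/49 | Shift at 24/32 |
|---|---|---|
| 5 points | 2.4 | 3.8 |
| 10 points | 4.9 | 7.5 |
| 20 points | 9.8 | 15.0 |

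The last column applies if recruitment stopped at the interim analysis with 32 ferric maltol children aged 2 to 17 and both PK quotas full (24/32 = 75%).

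**6. Recall alone, also assumed.** Let a proportion p have an early event, let a fraction r of these still be reported at Day 28, and let 20% have a later event independently. The shift is (24/49) × 0.8 × p × (1 − r). For p = 10% and r = 0.9 it is 0.4 points; for p = 40% and r = 0.7 it is 4.7 points.

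**7. Scale.** At 49 v 49, the standard error of a difference at 50% incidence is √(2 × 0.25/49) = 10.1 points. The 95% half-width, 1.96 × √(2p(1 − p)/49), is 15.8 points at 20% incidence and 19.8 points at 50%.

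**8. Pooling infants.** SAP 3.6 tabulates by treatment received and states no age split. All infants who enter treatment have Visit 3. With 12 of them in the ferric maltol column, the share is (24 + 12)/(49 + 12) = 36/61 = 59%.

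**The case against.** The best defence is that ascertainment differs in timing and is not missing. Every child is asked at Visits 4 to 7, and Protocol 11.2 requires all events from first dose onward to be reported. The other 25 ferric maltol children follow the ferrous sulfate schedule exactly. PK sampling of the test product alone follows from the PK objectives. All of this stands, and it confines the problem to recall of mild, short-lived early events and to procedural events. Serious events and discontinuations should be little affected.

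SAP 3.6.1 also tabulates drug-related TEAEs, and every overview category by system organ class and preferred term. Bruising and fainting can therefore be told apart from gastrointestinal events. This helps in part, but relatedness is an open-label judgement, and neither table touches the recall gap.

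Three stronger inferences are tempting:
- A reader might infer that the endpoint itself counts against ferric maltol, since Protocol 6.3 lists "Treatment-emergent Adverse Events leading to premature discontinuation of study drug/PK assessments from baseline to Week 12" and a ferrous sulfate child has no PK assessments to discontinue. The analysis text does not support this: the Synopsis statistical methods, Protocol 12.2.1, SAP 3.6 and the SAP 3.6.1 overview all limit the comparison to discontinuation of study drug.
- A reader might infer one-sided adherence coaching. Both arms have compliance reminders at Visits 2, 4, 5 and 6 and keep dosing diaries. Visit 3 adds one reminder and one assessment, whose effect on exposure could go either way.
- A reader might infer that a real tolerability advantage will be hidden. The documents show neither an advantage nor the size of the effect.

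**Conclusion.** The imbalance is real: 49% against 0% of children have an early adverse event enquiry, contacts average 5.49 against 5.00, and six PK samplings fall on one arm only. Neither document balances or separates this in the comparison. The likely direction is more recorded TEAEs on ferric maltol, because extra questions and needles tend to add reports. The amount cannot be estimated from the documents. The range of 2.4 to 9.8 points rests entirely on the assumed 5 to 20 points, and even its top is about one standard error of the difference. No test, margin or error rate is involved, so this concerns how the incidences are read and does not invalidate the comparison.

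The 24 is itself not stated consistently. Protocol 10.2 (footnote 2) refers to the first 12 children aged 2 to 17, which would give 12/49 = 24%; Protocol 10.3 and SAP 2.2.4 give 24. The imbalance is one-sided on either reading.

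**What to change.** 1. **For children still to be enrolled,** add a Day 7-10 telephone adverse event contact for every 2-17 year subject, in either arm, who has no Visit 3. Visit 7 is already done by telephone. The cost is one short call per child, at most 98 − 24 = 74. The documents do not say whether recruitment is open, and the call cannot repair the children already treated, who include the first-enrolled PK subset.

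2. **In SAP 3.6, before database lock,** keep the all-events table and add a sensitivity table of TEAEs and gastrointestinal TEAEs, by system organ class and preferred term, in three columns: ferric maltol with PK, ferric maltol without PK, and ferrous sulfate. Include a comparison limited to children randomised after the 12-child PK quota in their age group was filled, when both arms follow the same schedule. Because Protocol 9.3 allows PK replacements, define the cut as the enrolment of the last PK child in that age group. The cost is precision. With about 49 − 24 = 25 per arm, the 95% half-width at 50% incidence is 1.96 × √(2 × 0.25/25) = 27.7 points, against 19.8 for the full arms. The table needs a footnote saying so, and saying that the PK and non-PK columns also differ in calendar time.

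3. **Show any table that omits events first reported at Visit 3 only as a bound.** It would delete a Day 3 event in a PK child but keep the same event in a ferrous sulfate child who reports it at Visit 4, which favours ferric maltol. Excluding events attributed to PK procedures is not a clean substitute: Protocol 11.3.2 grades causality against study treatment only, and 11.1.2 defines procedure-relatedness only for serious events.

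4. **Wording.** Align Protocol 6.3 and SAP 2.3.1 with the study-drug wording of Protocol 12.2.1 and SAP 3.6, and reconcile the PK subset size in Protocol 10.2 with Protocol 10.3 and SAP 2.2.4. Neither change needs new data.
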